**Objectives: To study the effects of MDMA on responses to affective touch in individuals with a range of autistic traits**

### **Background and Specific Aims:**

Autism spectrum disorder (ASD) affects an estimated 2.47% of U.S. children and adolescents (Xu et al. 2018), leading to significant reduction in quality of life and millions of dollars in disability costs (Beuscher et al. 2014). Although medications have been used to treat individual symptoms of the disorder, there are no accepted pharmacological treatments for ASD. ASD is characterized by repetitive behaviors, communication difficulties and, importantly, social deficits. One manifestation of the social and communication deficits is a hypo-responsiveness to pleasantness of 'affective touch' (Voos et al. 2012, Kaiser et al. 2015, Cascio et al. 2012). Identifying the brain processes underlying reactivity to affective touch could provide an opportunity to elucidate the neural circuits involved in the disorder, and to develop effective new treatments.

Two classes of medication that have been proposed as potential treatments for ASD are those targeting the oxytocinergic and serotonergic systems. Several studies have examined the effects of oxytocin on ASD symptoms, but the findings have been mixed, perhaps because intranasal oxytocin does not readily enter the brain (Guastella and Hickie 2016). In one recent randomized controlled clinical trial in adults with ASD, intranasal oxytocin enhanced gaze fixation on socially relevant stimuli (Yamasue et al. 2018), and in another study plasma levels of oxytocin predicted responsiveness to treatment (Parker et al. 2017). Other studies have examined the effects of selective serotonin reuptake inhibitors (SSRIs) in the treatment of ASD but the results have been mostly unsuccessful (Autism Speaks 2009). Yet, recent evidence with rodents suggests that manipulating serotonin may enhance social behaviors. For example, in a preclinical model of ASD, direct activation of 5HT-1B neurons in the nucleus accumbens enhances social behavior (Walsh et al. 2018). Thus, there is suggestive evidence that both oxytocin and serotonin signaling may be important targets of medications for ASD, but neither system has yet led to effective treatments.

Our laboratory has conducted a series of behavioral studies with the psychostimulant drug ±3,4-methylenedioxymethamphetamine (MDMA), a drug that rapidly increases both oxytocinergic and serotonergic signaling. MDMA increases synaptic levels of serotonin, and increases plasma levels of oxytocin to a greater extent than intranasal administration of oxytocin itself (Kirkpatrick et al. 2014). Behaviorally, MDMA facilitates social behaviors, including those implicated in ASD, in both rodent models and healthy human volunteers (Kamilar-Britt and Bedi 2016), suggesting that it may have potential in the treatment of autism. Indeed, one recent study reported that MDMA reduces social anxiety in individuals with autistic traits (Danforth et al.

2018). To date, however, no controlled laboratory studies have investigated the neurobiological actions of MDMA in individuals with autistic traits, and little is known about how the drug affects behavioral indices of the social communication deficits, such as affective touch. We propose to address this gap in knowledge by testing the acute effects of MDMA, compared to placebo, on subjective, neural, and hormonal responses to affective touch in individuals with mild autistic-like traits.

**Specific Aim 1: To determine the effects of MDMA on subjective responses to affective touch in individuals with a range of mild autistic-like traits**

Our preliminary data suggest that MDMA enhances pleasantness ratings of affective touch in healthy adult volunteers (Bershad et al. 2019). Here we will extend this finding to individuals with symptoms of ASD. Adult volunteers with a range of mild autistic-like traits (N=45) as measured by the Autism Spectrum Quotient (ASQ) will attend two laboratory sessions during which they will be given placebo or 1.5mg/kg MDMA (oral). At the expected time of peak drug effect, they will complete behavioral tasks assessing responses to affective touch. We hypothesize that individuals with higher ASQ scores will rate the pleasantness of affective touch lower than those with low ASQ scores, and that MDMA will ameliorate this effect, increasing pleasantness ratings to levels similar to those of the low ASQ group without MDMA.

**Specific Aim 2: To determine the effects of MDMA on neural responses to affective touch in individuals with a range of autistic traits.**

fMRI studies indicate that individuals with autistic symptoms exhibit reduced responsiveness to affective touch in the orbitofrontal cortex (OFC) and superior temporal sulcus (STS), and individuals with diagnoses of ASD show reduced activity in these regions as well as in the bilateral insula and other regions involved in social and emotional processing (Voos et al. 2012, Kaiser et al. 2015). To understand the mechanism by which MDMA increases reactivity to affective touch, we will use functional magnetic resonance imaging to test the effects of the drug on BOLD responses to affective touch in individuals with a range of autistic traits. We hypothesize that individuals with high scores on the ASQ will exhibit reduced OFC, STS, and insular responses to affective touch, and that MDMA will enhance touch-related activity in these regions, correcting these deficits.

**Specific Aim 3: To determine the mediating role of oxytocin in the effects of MDMA on responses to affective touch in individuals with a range of autistic traits**

MDMA has been shown to increase plasma oxytocin, raising the possibility that oxytocin mediates the enhancement of social behavior induced by MDMA. Here we propose to assess whether the MDMA-induced rise in plasma oxytocin predicts enhanced responses to affective touch.

**Methods:**

**Design:** The study will use a 2-session within-subjects double blind design in which participants will receive MDMA or placebo in randomized order. Participants will vary in scores on the Autism Spectrum Quotient (ASQ). On each of two 4.5-hour sessions participants will first report to the Human Behavioral Pharmacology Laboratory suite for drug administration, and then they will be escorted to the MRI Research Center (MRIRC) for the fMRI scan. Subjective ratings will be obtained at regular intervals throughout the session and performance on the tasks, as well as neural measures of activation, will be obtained during the scans.

**Subjects:** 45 healthy volunteers (22 male, 23 female; age range 21-40 years) will participate in the experiment. Sample size was determined with a power analysis on preliminary data showing

MDMA increases pleasantness ratings of touch ( $d=0.44$ ). Recruiting 45 subjects will provide greater than 80% power to detect an effect. Based on our previous rates of participants completing all four sessions after enrolling in the study, to recruit 45 subjects, we will need to consent 60 participants. Subjects will complete the Autism Spectrum Quotient (ASQ), and we will recruit individuals with a range of scores on the questionnaire, with 15 each from the 0-10 range, 10-20 range, and 20-32 range. Subjects with clinically significant ASD, as determined by our screening interviewers and the participants' responses to questions during the psychiatric screening interview will not be included in the study and will be referred for treatment. In particular, any participants who have difficulty understanding or complying with the study requirements will be ineligible. Subjects will also complete the Social Anxiety Questionnaire (Caballo et al, 2012). All participants will be recruited without regard to race, religion or ethnicity through posters, advertisements and word-of-mouth referrals. Candidates will be screened in accordance with our general screening protocol, approved by the IRB under Protocol #13681B, which includes a physical, EKG, psychiatric screening interview and detailed drug use history questionnaire. We will enroll individuals who report having used ecstasy at least 4 times but not more than 40 times, with no adverse responses. Because MDMA will be administered as part of the study, the following populations are excluded for safety reasons: Individuals with a BMI  $<19$  or  $>30$ , or weighing under 130 lbs, as this alters dosing requirements; Individuals with high blood pressure, abnormal EKG, any medical condition requiring regular medication, or any other medical contraindication to MDMA administration as determined by our study physician; Individuals with a current (within the last year) DSM-IV Axis I diagnosis, excluding non-treatment seeking drug abuse; Individuals with a history of dependence on stimulant drugs; Women who are pregnant. Smokers smoking more than 25 cigarettes per week will also be excluded, to avoid confounding the effects of nicotine withdrawal with the effects of the study drugs/procedures, as participants will not be allowed to smoke during the sessions. The self-report questionnaires we use require fluency in English, and have not been translated and validated in other languages, thus individuals with less than a high-school education or those not fluent in English will be excluded.

### **Procedure**

Orientation: Participants who meet criteria will first be scheduled for an orientation session. During this session, subjects will be informed that the capsules used in the study may contain a placebo, stimulant, a sedative/tranquilizer, or a cannabinoid/marijuana-like drug. This range of drug types is included to minimize expectancy effects. Participants will be given an oral description of the study procedures and the written consent form. After the experimenter reviews this information and the consent form with the subject, and answers any questions he/she may have, subjects will sign the informed consent document. Abstention from recent drug and alcohol use will be verified by breathalyzer and urine drug tests. Subjects will be asked about possible claustrophobia, and they will complete the scanning questionnaire to ensure that they have no metal implants.

Study Sessions: Two 4.5-hour sessions will be conducted, separated by at least 72 hours. Please see below for a full timeline of the study sessions. On study session days, participants will arrive at 9am, and complete a urine and breath screening for recent alcohol and drug use, and a pregnancy test (for women). Participants will then complete Time 1 measures of subjective mood and drug effects, and complete these same measures periodically throughout the study (see below). Participants will ingest the capsule at 9:30am. For the next hour, while the drug is absorbed, they will be allowed to relax and watch a movie or read a book, but will not be allowed to do work. Subjects will be escorted to the MRIRC at 10:30am to undergo an fMRI scan while performing the Touch Task. The scan will last approximately 45 minutes. Participants

will then be escorted back to the lab, where they will remain, completing subjective measures of the drug effect every hour until at least 1:30pm (when we expect drug effects will end), or until the effects of the drug return to baseline (as measured by both subjective report and cardiovascular variables).

#### Timeline

9:00 am – Participant arrival, drug, alcohol and pregnancy testing, snack provided  
9:15 am – Time 1 Measures – POMS, DEQ, VAS, Blood Pressure, HR  
9:30 am – Administration of capsule  
10:00 am – Time 2 Measures - POMS, DEQ, VAS, Blood Pressure, HR  
10:30 am – Time 3 Measures - POMS, DEQ, VAS, Blood Pressure, HR  
11:00 am – fMRI scan with Touch Task  
11:45 am - end of scan  
12:30 pm – Time 4 Measures – POMS, DEQ, VAS, Blood Pressure, HR  
1:00 pm - Time 5 Measures – POMS, DEQ, VAS, Blood Pressure, HR  
1:30 pm - Participant leaves lab

End of study phone call: After the subject's last session we will conduct an end-of-study interview by phone. Participants will be asked to indicate how much they liked each study drug and how much they would want to take each drug again. Participants will also be asked to report which type or types of drugs they think they received at each session. Finally, participants will be told the study hypotheses, methods and the types of drugs that they received, and will be given a chance to ask any final questions.

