**2. Study drugs:**

Common side effects of MDMA include increased heart rate and blood pressure; bruxism; mydriasis; mild sensory and perceptual impairment; dryness of the mouth; difficulty concentrating; nausea; confusion; shakiness or tremor; changes in appetite; anxiety or panic attacks; and insomnia. We have used similar doses of MDMA in previous studies without adverse reactions (Bedi et al, 2009). The side effects of methamphetamine are similar, including increases in heart rate or blood pressure, dizziness, restlessness, tenseness, anxiety, nervousness, headache, diarrhea, sweating, constipation, difficulty sleeping, and dry mouth. These doses are unlikely to cause adverse effects in participants such as ours who are carefully screened for psychiatric and medical problems, and who report having used ecstasy previously without adverse effects. Participants will be monitored during experimental sessions for any symptoms of adverse effects, and a physician will be on call during and after sessions. To reduce the risk of hyperthermia sometimes associated with recreational use of ecstasy, we will keep room temperature low and provide subjects with water during study sessions. To prevent risk of hyponatremia due to excessive water intake, we will monitor water consumption during sessions, and participants will be restricted to consuming no more than one pint of water per hour after capsule administration and weighed to ensure that they are not retaining excessive fluids. Given these precautions, and the absence of evidence of the development of these conditions as a result of MDMA administration in controlled settings, we believe that administration of MDMA in the context of this study poses a low risk to participants. The doses selected for this study have been given to subjects in at least 29 previous studies, and no serious adverse effects were reported with these and even higher doses of MDMA (for review see Dumont and Verkes, 2006). Chronic use, or high doses of MDMA, have been shown to cause damage to brain cells in laboratory animals. However, this is unlikely at the doses subjects will receive in this study (see Vollenweider et al., 1999). Although any exposure to drugs with potential for abuse may entail some risk for development of problems of abuse, this is extremely unlikely in view of the low doses and limited number of drug exposures, the careful screening of subjects, and the laboratory setting in which studies are conducted. Subjects will receive

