**Subject time commitment and compensation:** The orientation typically takes approximately one hour. The two study sessions are estimated to last 4.5 hours each, for a total of 10 hours spent in study sessions. Participants are compensated \$10 for the orientation session and \$40 for each study session, with a bonus of \$60 for completion of all study sessions, giving a total of \$150.

**Data and Safety Monitoring:** The PI will monitor data collection and safety at weekly staff meetings. During these meetings, the PI will review and respond appropriately to (1) data collection and storage practices and (2) any adverse or unexpected effects from the study drugs. Both the study physician and PI will monitor the safety of study participants on an ongoing basis. The physician connected with this study will be on call during the experimental

sessions and for 24 hours after sessions. Subjects will be given telephone numbers for the study physician and investigators in case they experience unpleasant effects after leaving the laboratory. If a serious or unexpected adverse event were to occur, the staff member most closely involved with the subject at that time or the physician would notify the PI immediately. The PI would then take appropriate action and communicate with all necessary offices within the University and the FDA.

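### No contact after discharge is described as asking every participant about adverse effects, so delayed effects such as insomnia depend on spontaneous reports

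*Combined protocol and SAP*

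**What the plan says.** Risk to subjects, item 2 (Study drugs), gives a list of common MDMA side effects that ends with "changes in appetite; anxiety or panic attacks; and insomnia". On surveillance, the same item says: "Participants will be monitored during experimental sessions for any symptoms of adverse effects".

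The Procedure section fixes dosing: "Participants will ingest the capsule at 9:30am". The last scheduled assessment in the Timeline is "1:00 pm - Time 5 Measures – POMS, DEQ, VAS, Blood Pressure, HR", and the day closes with "1:30 pm - Participant leaves lab". The Procedure section makes that departure time a minimum, since participants remain "until at least 1:30pm (when we expect drug effects will end), or until the effects of the drug return to baseline", judged on subjective report and cardiovascular readings.

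Two scheduled contacts can follow a discharge.

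- **Session 2**, at least 72 hours after session 1. Before the capsule it lists drug, alcohol and pregnancy testing, POMS, DEQ, VAS, blood pressure and heart rate. The consent section adds a verbal re-check of consent.
- **The end-of-study call**, after the last session, with no interval given. Its first item is "Participants will be asked to indicate how much they liked each study drug and how much they would want to take each drug again". It goes on to drug guesses, disclosure of hypotheses and drugs received, and final questions.

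For the time after discharge, Data and Safety Monitoring provides a route that the participant must start: "Subjects will be given telephone numbers for the study physician and investigators in case they experience unpleasant effects after leaving the laboratory". A physician is on call for 24 hours after each session, and the PI reviews adverse or unexpected effects at weekly staff meetings.

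**The concern.** Two of the side effects that the protocol itself calls common, insomnia and changed appetite, can appear or continue after a morning session is over. The plan observes actively while participants are in the laboratory and then waits to be told. Spontaneous reporting usually finds fewer events than direct questioning, and what it finds depends on how readily each participant picks up the telephone.

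Two things follow. The PI's weekly review has no described source for the period after discharge other than what participants volunteer, so an absence of reports could be misread as an absence of effects. Ascertainment may also differ by treatment order. Someone given MDMA first returns to the laboratory at session 2, while someone given MDMA second has only a call at an unspecified time.

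**Working it through.** The plan states no adverse-event rate to reproduce, so the check sets the observation times against the listed effects and then goes through each contact.

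**1. Length of scheduled observation.** Inputs are the clock times in Procedure and Timeline.

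- Session length: 13:30 − 9:00 = 4.5 h, which agrees with the stated 4.5-hour session.
- Capsule to last scheduled measures: 13:00 − 9:30 = 3.5 h.
- Capsule to scheduled departure: 13:30 − 9:30 = 4.0 h, a minimum because the stay can be extended.

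**2. Where first-night insomnia would fall.** The documents give no bedtime. Assume a range of 9 pm to midnight.

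- After the capsule: 21:00 − 9:30 = 11.5 h, up to 24:00 − 9:30 = 14.5 h.
- After scheduled departure: 21:00 − 13:30 = 7.5 h, up to 24:00 − 13:30 = 10.5 h.

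Across this range sleep begins well after scheduled observation stops but within the 24-hour on-call period. The event can be reported that night or the next morning, but nobody is scheduled to ask about it.

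**3. What each instrument or contact would elicit.**

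| Contact or instrument | Described content | Asks about effects since the previous session? |
|---|---|---|
| POMS | Momentary mood | No |
| DEQ | Feeling, liking or disliking, and wanting more of the drug | No |
| VAS | Single items, including Dizzy and Restless | No; no sleep or appetite item listed |
| End of Session Questionnaire | Drug belief, wish to take it again | No |
| Session 2 arrival | Tests, Time 1 measures, consent re-check | None described |
| End-of-study call | Liking, wanting, guess, debriefing, final questions | None described |

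In the call, the participant's final questions are listed together with the disclosure of which drugs were given. Anything volunteered at that point may come from someone who already knows the allocation.

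**4. Extent.** With 45 completers and two sessions each there are 45 × 2 = 90 discharges, and none is followed by a described adverse-effect question. Assuming equal allocation to the two orders, 45 / 2 = 22.5, so about 22 or 23 participants receive MDMA at session 2 and have only the call afterwards.

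**The case against.** The best defence is that safety after discharge is not ignored. Participants have telephone numbers, a physician is on call for 24 hours, the PI reviews effects weekly, and the call invites questions. All of that stands. A reader might infer that insomnia cannot be captured at all, and the documents do not support that: first-night insomnia falls inside the on-call period and can be reported. The supportable statement is that its capture is passive.

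Second, a reader might treat 1:30 pm as a hard end to observation. It is not, because the Procedure section keeps participants until effects have subsided. Nothing suggests that this extension is meant to reach the first night.

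Third, a reader might infer that someone with a lasting reaction to MDMA at session 1 could be given MDMA again without being asked. The Design section describes one MDMA and one placebo session in random order, so that reading does not follow from the design. The risk section does speak of two doses of MDMA. That statement and the Design section need to be reconciled, but the present point does not depend on it.

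Fourth, the measures before the session 2 capsule could show persisting low mood, restlessness or raised blood pressure. That is fair, but they would not show an effect that had already resolved, such as one bad night.

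Fifth, the description of the call is a summary, and the consent pages and the separate screening protocol are not available here. Instructions on delayed effects may sit there. The point is therefore limited to what the protocol describes.

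Finally, side-effect rates are neither an aim nor a planned analysis. This is correct, and it limits the weight of the point.

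**Conclusion.** The point holds in a limited form. Adverse effects are actively sought only during sessions, with scheduled departure 4 hours after the capsule as a minimum. After discharge no described contact asks every participant about them. Delayed effects that the protocol lists as common, with first-night insomnia the clearest case, depend on spontaneous reports. The end-of-study call has no stated interval, so follow-up after MDMA is not comparable between the two orders.

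The size is modest. No hypothesis test, estimate or power figure changes. What is lost is a dependable count of delayed effects under MDMA and under placebo, and a firmer basis for the PI's safety review. The conclusion rests on three assumptions: the protocol's lists of session and call content are complete, bedtime lies between 9 pm and midnight, and the two orders are allocated equally (which affects only the figure of 22 or 23). It is best treated as an inexpensive improvement to data collection.

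**What to change.** Use the two contacts that already exist.

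1. At session 2 arrival, ask one open question about any unwanted effects since the previous session, followed by a checklist of the side effects in the risk section, including sleep and appetite.
2. Ask the same in the end-of-study call, placed before the participant is told which drugs were given, so that answers are not coloured by knowing the allocation.
3. State a fixed window for the call after session 2, so that participants in either order have a comparable period of follow-up after MDMA.
4. Record answers by session and include them in the PI's existing safety review.

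The cost is a few minutes at each contact and a few added sentences in the protocol, with no new visit or staff and no change to sample size. Reported side-effect counts will be higher than under spontaneous reporting alone, and any write-up should say that the effects were solicited. This changes data collection only and sets no rule for dosing or clinical management.
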